**Figure 3. Scheduling Scheme for Amputation Date and MSC Injections**

**Figure 4. Diagram of Injection Sites of BMAC in Below Knee Amputations (BKA).**

**Figure 4.**

Upper Leg and Gastrocnemius Muscle Injections: BMAC will be injected 2-3 cm. deep into the muscle at approximately 15 sites 3 cm apart medially and approximately 10 sites laterally, delivering 1 mL of BMAC at each site.

ATM Injections: BMAC (up to 3 mL) will be injected into the ATM below the anticipated point of amputation in up to 5 sites within the area of 3 x 10 x 3 cm.

#### **BMAC Administration: Anterior Tibialis Muscle.**

On the day of BMAC injection in the operating room of the Richard L. Roudebush VA Medical Center, the index limb will be marked for amputation. The injection site area is marked on the anterior compartment of the lower leg below the point of amputation. The BioCue™ product is injected along a 3 cm tract into the anterior tibialis muscle (ATM). The injection site(s) will be marked with permanent ink on the ATM. The BMAC suspension will be injected over 3 minutes with the needle retracted 5 mm simultaneously to permit infiltration into the muscle.

#### **Ability to Recover BioCue™ Injection Sites in Anterior Tibialis Muscle.**

Retrieval of the BioCue™ injection sites is accomplished at the time of amputation. The area demarcated by the surgical marker is excised for histological analysis.

Needle biopsies may be performed below the knee at the time of cell injections or above the knee at the time of amputation to obtain skeletal muscle samples for histological and biochemical analysis. There will be no additional MCS injections for this purpose.

**Baseline Screening and Follow-Up Schedule.** The following evaluations will be carried out at baseline to determine if the patient is eligible for study: (1) Baseline blood tests (complete blood count, serum chemistries, eGFR, hsCRP); (2) medical history and physical exam; (3) concomitant medications; (4) pregnancy test for women of childbearing age; and (5) 12 lead ECG; and (6) LEADs and/or TcPO2 of index leg, as indicated. In the interest of time to major amputation, we may collect data retroactively to determine eligibility. If eligibility can be determined based on recent prior clinical notes and laboratory values, we will use those values for our study purposes and omit corresponding tests from the baseline

evaluation. It will not be considered a protocol deviation if labs are not finalized prior to cell injection and amputation; subjects will still be able to participate in the study.

**Determination of survival of BioCue™ cells and Quantify angiogenic activity of transplanted BMAC cells.** Harvested ATM from each time point fixed in 4% paraformaldehyde will be embedded in paraffin and sectioned (5 $\mu$ m thickness). Using IHC, sections of ATM will be stained with fluorescent monoclonal antibodies against CD34 and CD133 to quantify Proangiogenic Hematopoietic Cells (PHC) at each injection site and each time point. We will further enumerate PHCs in ATM using multiparametric flow cytometry (MFC) for CD133 $^{+}$ CD34 $^{+}$ CD45 $^{+}$ CD16 $^{-}$ CD14 $^{-}$ CD235 $^{-}$  cells, as previously described. Hypoxia-inducible factor-1 $\alpha$  (HIF-1 $\alpha$ ), will be quantified and localized in ATM sections with immunostaining, as previously performed in ischemic human muscle. mRNA for HIF-1 $\alpha$ , VEGFF, PDGF, and FGF will be quantified using qPCR. Chemokine protein expression from muscle homogenates and plasma from blood samples will be further quantified with multiplex chemokine analyte panels and liquid chromatography-mass spectrometry (LC-MS), focusing on Angiogenin, Angiopoietin-1, Angiopoietin-2, Endostatin, FGF (acidic and basic), PDGF-AA, PDGF-BB, PIGF, Thrombospondin-2, VEGF, VEGF-D, Activin, Follistatin, GCSF, TGF-B, SDF-1, and HGF, in addition to other proteins associated with the BioCue secretome, as previously reported.

Capillary density will be quantified using IHC for CD31. Angiogenic and inflammatory cytokines will be quantified using multiplex protein arrays from muscle homogenates and peripheral blood samples (collected at baseline through week 24 follow up visit). Comparison between BioCue™ injection sites and controls will be made. Levels of circulating cytokines from peripheral blood will be compared to baseline. Changes in skeletal muscle morphology will be described as compared to healthy controls. It will not be considered a protocol deviation if peripheral blood specimens are missed or outside the window ranges of study visits.

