The BioCue™ Blood and Bone Marrow Aspirate (BMAC) Concentration System is used to process blood and bone marrow aspirate to produce an autologous PRP output for use in autograft and/or allograft therapies. The BioCue™ device is the exact same device as the MarrowStim™ PAD Kit that was used to treat subjects in prior versions of this protocol. Treatment includes removal of approximately 300 mL of bone marrow from the patient's posterior or anterior iliac crest, which is then mixed with an anticoagulant solution and processed in the BioCue™ device to concentrate the autologous bone marrow cell suspension for delivery. The subsequent treatment utilizes this BMAC at the point of care by injection to multiple sites in the affected leg. The BioCue™ BMAC product is hypothesized to function via angiogenic mechanisms. To date there are no comprehensive descriptive analyses of the fate of BioCue™ BMAC cells after transplantation in human tissue. Thus we propose a pilot trial, **Safety and Efficacy of Concentrated Autologous Concentrated Bone Marrow Aspirate (BMAC) in Preventing Wound Complications in Amputations (The MarrowCHAMP Study)**, that will help discern the mechanisms of therapeutic action in man. MarrowCHAMP will address two critical areas simultaneously:

assessing the efficacy of BMAC in preventing wound complications in lower extremity amputations and providing tissue at BioCue™ injections sites from a controlled time-point for first in man biochemical and histological analyses.

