**Characterize the host tissue response to, paracrine activity of, and fate of transplanted BMAC.**

Patients will undergo amputation and injection sites at the anterior tibial muscle (ATM) will be harvested at that time. Collection of up to 10 cm of the soleus muscle will serve as control. IHC staining will determine capillary density and local host immune responses. Angiogenic and inflammatory cytokines will be quantified using a multiplex array system and quantitative PCR.

The expected outcomes will provide the framework for the design of a Phase II randomized clinical trial and critical insights that may direct a future trial to test multi-dosing regimens. This investigation will establish a unique clinical model that can expedite safety and mechanistic analyses of projects in PAD that include bioscaffolds to enhance cell survival.

**Determine the effects of chronic limb ischemia and diabetes on nerve function and to assess the effects of mesenchymal stem cell administration on their function.** Peripheral nerve tissue (sciatic, femoral, tibial, sural and/or plantar nerve segments) will be collected at the time of amputation from the amputated portion of the lower limb. Patients with critical limb threatening ischemia, particularly with diabetes, have polyneuropathies that alter motor unit engagement and peripheral sensation leading to ambulatory dysfunction and pressure ulceration of the foot.

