#### **6.1.3 Handling, storage, accountability**

Autologous heparin-anticoagulated bone marrow aspirate (360 ml) is loaded into 6 Biocue™ separators through their center ports. The separators are placed into the centrifuge and spun at 3,200 RPM for 15 minutes. Following centrifugation, the BMAC containing the nucleated cells is re-suspended within the fixed volume of fluid. The BMAC is then recovered from the separator by connecting a syringe to the red capped port and extracting the contents. All steps (marrow harvest, BioCue™ processing, BMAC administration) are performed at the point-of-care within a single procedure.

Output characterization will be performed on a sample from a single BioCue™ separator chosen randomly. A sample will be pulled from one tube, assuming it is representative of all tubes. The number of cells will be enumerated from one separator and multiplied by six (6). In the case that a positive culture should result from the BioCue™ product, the PI will notify the patient and schedule an examination within 48 hours. The patient will be assessed for evidence of infection including evidence of erythema at the site of the injection, fever (temperature > 100.9 F), and/or leukocytosis (white blood count >11K). In the event of these clinical and laboratory findings, the appropriate antibiotic or antifungal agent will be instituted based on the culture results and recommendations of an Infectious Disease specialist. Follow up examinations and laboratory work will be scheduled based on the severity of symptoms and laboratory findings at the discretion of the PI and per Indiana University School of Medicine procedures.

Sterility testing of the BioCue™ output will be performed in accordance with 21 CFR 610.12. This information will be recorded on a source document and kept in the subject's research chart. Bone

marrow samples remaining after cell characterization may be subject to additional assessments by outside laboratories. Any samples sent outside the site will be identified by subject number only and will not contain any identifying information.

All sterility failures will be reported to the IRB and FDA as adverse events within 30 calendar days. The report will include results of the investigation into the cause of the event and any and all corrective actions taken to mitigate risks to future study subjects.

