Following the BioCue™ procedure, laboratory analyses will be performed on unconcentrated and concentrated bone marrow aspirate samples. Total white blood cell (WBC) count, mononuclear cell (MNC) count, mononuclear cell recovery (concentrated MNC/unconcentrated MNC), granulocyte count, platelet count, cell viability, and cell purity (MNC/WBC) will be recorded. In addition, total aspiration volume, total BioCue™ input volume, total BioCue™ output volume, and total delivery volume will be recorded. Additional information, such as CD marker characterization, may also be performed.

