**Exploratory Efficacy.** Continuous confidence intervals at the 95% level will be constructed to explore the effect of administration of BMAC on the composite endpoint at 6-months of death, revision of amputation and gangrene, and will be compared to historical cohorts at our institution. The null hypothesis of no change will be rejected if the pairwise confidence intervals does not include zero. The critical levels for the multiplicity adjustment will be determined by simple Monte Carlo simulation.

Quantities over time of BMAC will be fit to an exponential decay curve using a residual pseudo-likelihood procedure and cell half-life ( $\lambda$ ) will be estimated. Binomial confidence Intervals at the 95% confidence level and *p*-values for these four groups after BMAC transplantation will be calculated for the presence or absence of MHC expression and SDF-1 activation. Continuous confidence intervals at the 95% level will be constructed to explore the differences among the time-tiered administration of BMAC for (1) the CD34+CD133+ pro-angiogenic hematopoietic cells recruitment of HIF-1 $\alpha$ /SDF-1/CXCR4 to ischemic muscle, (2) the quantify of capillary density in muscle fibers using hematoxylin phloxin saffron and CD31 counts, (3) VEGF-A,C,D, hepatocyte growth factor, angiopoietin-1 to characterize angiogenic cytokine expression, (4) percent coverage, fiber diameter and cross-sectional area to examine changes in morphology. The correlation between capillary density (CD31 counts) with tissue perfusion (ICA) for each time point will be estimated by Spearman's rank coefficient.

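### CD34/CD133 counts in injected muscle do not isolate the graft, so the fate part of the second objective and the Section 9.3 cell half-life are not identified

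*Combined protocol and SAP*

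**What the plan says.** The second objective, in the Synopsis and Section 3, is: "Characterize the host tissue response to, paracrine activity of, and fate of transplanted BMAC". Fate is one of its three parts.

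The Introduction describes a device used to "concentrate the autologous bone marrow cell suspension for delivery", so donor and recipient are the same person. Section 6.1.3 states: "All steps (marrow harvest, BioCue™ processing, BMAC administration) are performed at the point-of-care within a single procedure". Neither that section nor the device description in Section 2.1 contains a labelling step, and none appears elsewhere.

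Section 7.1 has a paragraph headed "Determination of survival of BioCue™ cells and Quantify angiogenic activity of transplanted BMAC cells". Its cell-identifying measurements are two. First, "sections of ATM will be stained with fluorescent monoclonal antibodies against CD34 and CD133 to quantify Proangiogenic Hematopoietic Cells (PHC) at each injection site". Second, "We will further enumerate PHCs in ATM using multiparametric flow cytometry (MFC"), on a CD133+CD34+CD45+ phenotype negative for CD16, CD14 and CD235. The paragraph's other read-outs are HIF-1α, mRNA, chemokine and cytokine protein, and CD31.

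Section 9.3, under Exploratory Efficacy, lists "the CD34+CD133+ pro-angiogenic hematopoietic cells recruitment of HIF-1"α/SDF-1/CXCR4 to ischemic muscle among its comparisons. It also plans to fit amounts of BMAC over time to an exponential decay curve and to estimate a cell half-life. Section 9.1 mentions quantification of the product between sites. Neither section says which assay measures the amount of BMAC.

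Section 3 names soleus muscle as the tissue control, and Sections 7.1 and 9.1 compare injected sites with control. For the product itself, Section 6.1.3 requires white cell, mononuclear, granulocyte and platelet counts, but for surface markers it says only: "Additional information, such as CD marker characterization, may also be performed".

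**The concern.** To report survival or half-life of a graft, some measurement must distinguish an injected cell from a host cell. In an autologous transplant, genotype and HLA cannot do that. CD34 and CD133 mark a cell type, and they do not show whether a cell was injected a week earlier or arrived from the circulation. Section 9.3 treats the same phenotype as recruited, so the plan itself allows for such cells to arrive.

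A high count at the injected site is therefore compatible with good graft survival, with strong recruitment, or with any mixture. These are different mechanisms. The Introduction presents the fate of these cells as a gap in knowledge that the trial will help to fill, and Section 3 says the results will frame a Phase II trial. A half-life reported from these counts could enter that design as a property of the graft when it is not one.

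**Working it through.** The plan states no half-life, persistence fraction or power for this objective, so there is no figure to reproduce. The check is whether the planned measurements identify the quantity of interest.

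**Model.** Let B be resident (background) CD34+CD133+ cells, R host cells recruited because of the injection, and G persisting injected cells.

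- Injected site (tibialis anterior, Section 7.1): B + R + G
- Control (soleus, Section 3): B, assuming that a different, uninjected muscle has the same background

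The coefficient rows for (B, R, G) are (1, 1, 1) and (1, 0, 0). The rank is 2 for 3 unknowns. Injected minus control gives R + G and nothing finer. Flow cytometry of the same phenotype repeats the first row and adds no rank.

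**What would add information.**

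- A graft-specific measurement adds the row (0, 0, 1). The rank becomes 3 of 3, and G is estimable.
- A vehicle-injected site alone does not suffice. Split R into needle-induced and cell-induced recruitment. The unknowns are then 4, and the rows (1, 1, 1, 1), (1, 0, 0, 0) and (1, 1, 0, 0) have rank 3. A graft-specific row is still needed to reach 4.

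**Size, by illustration.** Take one harvest at 7 days (Synopsis). Let c be the excess over control as a fraction of injected CD34+CD133+ cells, and f the share of that excess that is recruited. The documents give neither, so both are assumptions. The calculation also treats the injected number as known and recovery as complete, which favours the plan. Under exponential decay:

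half-life = 7 × ln 2 / ln(1 / [c(1 − f)])

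Example: c = 0.10 and f = 0.90 give c(1 − f) = 0.01, so the half-life is 4.852 / 4.605 = 1.05 days.

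| Excess c | f = 0 | f = 0.50 | f = 0.90 | f = 0.99 |
|---|---|---|---|---|
| 0.05 | 1.62 d | 1.32 d | 0.92 d | 0.64 d |
| 0.10 | 2.11 d | 1.62 d | 1.05 d | 0.70 d |
| 0.20 | 3.01 d | 2.11 d | 1.24 d | 0.78 d |
| 0.50 | 7.00 d | 3.50 d | 1.62 d | 0.92 d |

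Within a row the observed count is the same and every half-life fits it. At f = 1 no graft survives. Across rows, an excess of 0.50 with f = 0.90 and an excess of 0.05 with f = 0 both give 1.62 days, so a tenfold difference in count need not mean any difference in graft survival. More subjects would tighten the estimate of R + G and would not separate its two terms.

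**The case against.** **The text does not equate the count with surviving product.** This is fair. The staining sentence in Section 7.1 says only that the cells will be quantified. Section 9.3 does not use the word host, and its recruitment phrase is garbled. A reader might infer that the protocol labels one number as graft survival in one place and as host response in another; it does not say so expressly. The point does not need that reading. The staining and its flow-cytometry counterpart are the cell-identifying assays under a heading about survival, and they would not isolate the graft even if the recruitment phrase were absent.

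**A label may exist.** That the cells are unlabelled is inferred from silence. If a tracer is used, the survival analysis depends on it and the protocol should describe it.

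**There are controls.** The soleus sample, and the optional below-knee biopsy at injection, address background. This stands, and it makes the total excess over control estimable. It does not split that excess.

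**Counting the injected cells would at least bound persistence.** A reader might infer that harvest count divided by injected count is an upper bound. The documents do not support this. It would require all injected tissue to be recovered and counted, no graft cell to have left the area, and every survivor to carry both markers. The plan excises the marked area, stains 5 µm sections, and injects a concentrate whose other nucleated cells are not counted by this phenotype. The ratio can therefore fall below true persistence. The denominator is weak as well: cells are counted in one separator and multiplied by six, total delivery volume is recorded with no separate figure for the tibialis anterior, and the volume for that muscle is up to 5 mL in Section 3 but up to 3 mL in Section 7.1. Those two passages must be reconciled in any case.

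**This is an exploratory pilot.** Small size excuses imprecision, but not a quantity that the measurements cannot identify.

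**Conclusion.** The point holds for the fate part of the second objective, for the survival read-out in Section 7.1 and for the half-life in Section 9.3. With the planned measurements, only persisting plus recruited CD34+CD133+ cells can be estimated, and even that assumes soleus is a fair background for tibialis anterior. Graft survival and half-life are not identified at any sample size. In the illustration with a 10% excess, one count fits half-lives from 2.11 days down to 0.70 days at 99% recruited, and no surviving graft at 100%.

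A reader might go further and conclude that half of a principal objective, or the whole mechanistic programme, has no answer. The documents do not support that. Fate is one of three parts of the objective. Capillary density, cytokine, safety and clinical analyses do not depend on cell origin and are unaffected.

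The conclusion rests on two readings: that no graft-specific marker is used, because none is described, and that the undefined amount of BMAC in Section 9.3 would come from these counts, because no other cell-identifying assay of the muscle is described. A stated graft-specific assay would remove the problem.

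**What to change.** 1. **Section 7.1, survival paragraph.** Relabel the read-out as CD34+CD133+ cell density at the injected site versus control muscle at harvest, comprising persisting and recruited cells.
2. **Section 9.3, Exploratory Efficacy.** Drop the decay curve and half-life for BMAC, or restate them as a description of total CD34+CD133+ cells with no claim about graft survival.
3. **Synopsis, Introduction and Section 3.** Limit the fate wording to match, and state that graft persistence is not identified unless a graft-specific measurement is specified. The Section 3 remark about bioscaffolds and cell survival concerns other projects and should stay as it is.
4. **Optional, Section 6.1.3.** Make CD34/CD133 characterization of the product routine for future subjects, as descriptive product data. It cannot be assumed to exist for subjects already treated under prior versions. Do not report harvest count over injected count as an upper bound on persistence.

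Items 1 to 3 are wording changes. Their cost is a more modest mechanistic claim: the trial would no longer offer to answer the fate question unless the sponsor adds a measurement that identifies injected cells. Item 4 adds a marker panel on a product sample that Section 6.1.3 already takes, at the core flow cytometry laboratory named in Section 6.2.3.

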## **4 STUDY OVERVIEW**

### **4.1 Study Approach**

This protocol is designed to describe a Phase I single center open label trial study that will enroll up to 12 patients requiring semi-elective amputation within a 30-day period for complications related to CLI.

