**Table 3. Inclusion/Exclusion Criteria for Enrollment of Subjects**

Inclusion criteria	

1. Be <math>\geq 40</math> and <math>\leq 90</math> years of age.

2. Patients requiring lower extremity major amputation, as determined by an independent vascular specialist.

3. If ulceration or gangrene is present, it is distal to malleoli (to allow adequate length of ATM area of approximately 3 cm x 10 cm x 3 cm)

4. Amputation can safely be performed up to 30 days after screening, as determined by an independent vascular or orthopedic surgeon.

5. Females of childbearing potential must be willing to use one form of birth control for the duration of the study. Female participants must undergo a blood or urine pregnancy test at screening.

Exclusion criteria	

1. Patients who are pregnant, planning to become pregnant in the next 12 months, or lactating.

2. CHF hospitalization within the last 1 month prior to enrollment.*

3. Acute coronary syndrome (ACS) in the last 1 month prior to enrollment.*

4. HIV positive or active, untreated HCV as determined by review of medical records.

5. History of cancer within the last 5 years, except basal cell skin carcinoma.

6. Inability to provide written informed consent due to cognitive or language barriers (interpreter permitted).

7. Concurrent enrollment in another clinical investigative trial.

8. Any condition requiring immunosuppressant medications (e.g., for treatment of organ transplants, psoriasis, Crohn's disease, alopecia areata).

9. Presence of any clinical condition that in the opinion of the PI or the sponsor makes the patient not suitable to participate in the trial.

\*As defined by the standard definitions of CHF and ACS by the American Heart Association.

Participant Withdrawal Criteria	At the discretion of the investigator or at the request of the participant.
--	---

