## **9 STATISTICAL METHODS**

### **9.1 Determination of Sample Size**

The study is not powered for efficacy in preventing wound complications of revision of amputation. The maximum number of tissue specimens we hope to collect will be twelve (12). Quantification of BioCue™, capillary density and cytokines will be compared between injection sites (between escalating doses and control) using a paired Student's t-test. Serum cytokine levels post BioCue™ injection will be compared to baseline levels using a paired Student's t-test.

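### Muscle morphology has no workable comparator: section 7.1 names undefined healthy controls, section 9.3 names time tiers that one harvest does not provide, and the paired test in section 9.1 leaves morphology out

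*Combined protocol and SAP*

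**What the plan says.** The combined protocol and SAP deals with control tissue and morphology in several places.

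- **Section 7.1, paragraph on cell survival and angiogenic activity.** A general sentence says "Comparison between BioCue™ injection sites and controls will be made", without naming the control or the outcomes. Two sentences later morphology gets a comparator of its own: "Changes in skeletal muscle morphology will be described as compared to healthy controls".
- **Section 3, host tissue response objective.** The control tissue collected is named: "Collection of up to 10 cm of the soleus muscle will serve as control".
- **Section 7.1, recovery of injection sites.** The ink-marked area of the anterior tibialis muscle (ATM) is excised at amputation. Other muscle samples are optional: "Needle biopsies may be performed below the knee at the time of cell injections or above the knee at the time of amputation".
- **Section 9.1.** The paired test covers quantification of BioCue, and "capillary density and cytokines will be compared between injection sites (between escalating doses and control) using a paired Student's t-test". Morphology is not in this list. Twelve is given as the most specimens the investigators hope to collect.
- **Section 9.3, exploratory efficacy.** Percent coverage, fiber diameter and cross-sectional area are the morphology measures. They get 95% confidence intervals for differences among time tiers of BMAC administration. Healthy controls are not mentioned.
- **Population.** Section 4.1 says the trial "will enroll up to 12 patients requiring semi-elective amputation within a 30-day period for complications related to CLI". Table 3 requires "Patients requiring lower extremity major amputation, as determined by an independent vascular specialist".

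**The concern.** The second objective is to characterize the response of host tissue to transplanted BMAC. A morphology result serves that objective only if its comparator differs from the injected muscle mainly by the injection. Healthy muscle differs by ischemia, often by diabetes, possibly by age, and by BMAC, all at once. The contrast is also cross-sectional, so it does not measure a change.

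The error can run in either direction. A difference from healthy muscle may be entirely disease, and a real benefit may be hidden because treated ischemic muscle still looks worse than healthy muscle. Section 3 expects the results to provide the framework for a randomized Phase II trial, so a morphology readout that cannot be interpreted is a lost opportunity, though a small one.

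**Working it through.** The plan gives no effect size, standard deviation or power for morphology, and 12 specimens is a stated maximum without a derivation. There is no planned figure to reproduce. The main check is a comparison of the text, followed by two short calculations.

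**1. Can any comparator as written isolate BMAC for morphology?**

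| Place | Comparator for morphology | Does the protocol set it up? |
|---|---|---|
| 7.1, morphology sentence | Healthy controls | No source, number, muscle or matching. No eligible patient qualifies (4.1, Table 3), and Table 4 has no healthy-volunteer procedure |
| 7.1, general sentence | Injection sites versus controls | Soleus is collected (section 3), but this sentence does not name the control or mention morphology |
| 9.1 | Paired injection site versus control | Planned, but morphology is not listed |
| 9.3 | Time tiers of BMAC administration | One nominal harvest at about one week (7.1), so there are no tiers |

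Section 6.1.2 allows amputation sooner than one week in some cases. Harvest times may therefore vary between patients, but that is incidental variation and not a set of planned tiers.

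**2. What could a healthy-control contrast show when BMAC does nothing?** This is an illustration. The disease difference d (in SD units) and the number of healthy specimens m are assumptions, because the documents give neither. The BMAC effect is set to 0 and n = 12 injected specimens (the section 9.1 maximum). For a two-sample comparison with equal variances, the probability that the two-sided 95% CI excludes zero comes from the noncentral t distribution with

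- degrees of freedom n + m − 2,
- noncentrality d / √(1/n + 1/m).

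Example with m = 12 and d = 1: df = 22, critical value 2.074, noncentrality 1/√(1/12 + 1/12) = 2.449, probability 0.649.

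| Assumed disease difference | m = 12 | m = 6 |
|---|---|---|
| 0.5 SD | 22% | 16% |
| 1.0 SD | 65% | 47% |
| 1.5 SD | 94% | 80% |
| 2.0 SD | 99.7% | 96% |

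A clear difference from healthy muscle is therefore compatible with no BMAC effect at all.

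**3. What precision would a within-subject comparison have?** The 95% CI half-width for a mean paired difference, in units of the SD of the differences, is t(0.975, n − 1)/√n.

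- 12 complete pairs: 2.201/3.464 = 0.635.
- 6 complete pairs (an assumed lower figure): 2.571/2.449 = 1.05.

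These figures describe the precision of the replacement. They do not measure the bias in the healthy-control contrast.

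**The case against.** The strongest case on the other side has four parts.

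- **The sentence only promises a description.** A reader might infer that a difference from healthy muscle will be reported as a BMAC effect. The documents do not support that. No test or interval is attached to the healthy contrast, nothing attributes it to BMAC, and the interval analysis of morphology in section 9.3 does not use healthy controls. A healthy reference is also a legitimate way to describe diseased muscle. This stands. The problem is that no usable comparator is assigned, not that a false claim is planned.
- **The controls are undefined rather than absent.** A reader might infer that the trial has no healthy tissue. An archived or outside source is not described, but it is not excluded either. This stands.
- **A within-subject comparison may already be intended.** The general sentence in section 7.1 does not limit itself to particular outcomes, and soleus is collected as a control. This stands in part: such a comparison is not ruled out. It is not assigned to morphology either, which is then given a different comparator in the same paragraph.
- **The within-subject comparator is imperfect.** Soleus is a different muscle from the ATM, so for fiber size the contrast mixes muscle type with BMAC. The same leg also receives gastrocnemius injections, so soleus may be exposed. No sham injection controls for needle and volume injury. Only the ink-marked ATM is in the collection plan, and uninjected ATM may not exist for subjects treated under earlier versions. All of this stands. It would be wrong to say that a within-subject control removes every difference or comes free. It does hold patient, limb disease, diabetes and age constant, which healthy muscle cannot do.

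**Conclusion.** The concern holds as a gap and an inconsistency. Sections 7.1 and 9.3 give morphology different comparators, neither is set up by the protocol, and the paired comparison that could inform the tissue-response objective does not list morphology. A contrast with healthy muscle cannot separate BMAC from disease, whatever the number of healthy specimens. The probabilities above show this under assumed disease differences and are not estimates for this trial.

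The impact is limited to one exploratory, descriptive tissue outcome in an unpowered pilot whose primary attention is safety. No decision rule depends on it. The change is still worth making because it is cheap and replaces a comparison that cannot answer the objective with one that can partly answer it.

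**What to change.** State one comparator for percent coverage, fiber diameter and cross-sectional area, in the same terms in sections 7.1, 9.1 and 9.3. Suggested text:

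*Morphology at injected ATM sites will be compared within subject with control muscle from the same amputated limb, and reported as the mean paired difference with 95% CI for the pairs available. The control is the soleus sample and, where it can be taken from the amputated specimen, uninjected ATM away from the ink-marked area; the two are reported separately.*

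In addition:

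- Remove the time-tier comparison of morphology from section 9.3, or state which tiers exist.
- List any optional needle biopsy taken before injection as a supporting value.
- State the limits: soleus is a different muscle and may be exposed to nearby injections; needle and volume injury is not controlled; uninjected ATM may be missing for subjects already treated.
- Define the source, muscle and number of any healthy reference and label it as describing disease, not treatment effect. Otherwise drop it.

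The cost is a few sentences in three sections and a few extra tissue sections per limb. Uninjected ATM would be an added specimen, taken from a limb already removed. No extra patients or visits are needed.
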